Participants randomized to the MIAPP intervention will utilize their personal smartphones or tablets, or be provided with a smartphone for use during the study period if they do not have access to a personal device or choose not to use their personal device. The patient navigator or other research staff will help patients obtain a study phone when needed. Phones will be returned at the end of the study period. Participants needing a study phone will sign two copies of a [Phone Agreement Contract](#). If the study phone is lost, damaged, or stolen, there is no penalty to the participant; the study phone will be replaced up to one time. If the second phone is lost, damaged, or stolen, participants can continue to upload videos using a personal device if able and willing. Alternatively, they can continue participating in all remaining study procedures without uploading videos – i.e., they can receive a financial reward for linking to an outpatient buprenorphine provider, and they can complete the 30-day follow-up assessment. Participants who choose to utilize their own device will not be reimbursed for data plan costs and will utilize their device's memory.

Protection of Human Subjects

Involvement of Human Subjects

This study will conduct a randomized controlled trial of 40 participants with opioid and methamphetamine use at Harborview Medical Center (HMC) who are initiated on buprenorphine while in the hospital to determine effects of the intervention on post-discharge outcomes of linkage to outpatient treatment, retention on medication, use of opioids or methamphetamine, and hospital

readmissions and ED visits. Patients will be assigned to one of two arms (20 per arm) using a stratified randomization procedure.

Research Material Obtained from Participants

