Descriptive statistics will be calculated for all baseline variables; variables will be assessed for any differences between the two randomized arms using chi-square tests, t-tests, or the Mann-Whitney U test depending on the distributions. Baseline variables that differ between the two arms and potentially confound tests of intervention effects will be included in analyses as covariates. This study will use an intent-to-treat analysis including all subjects according to their randomized assignment, regardless of their follow-up status and their level of compliance with intervention components. The investigators will provide regular written reports to the Data Safety Monitoring Board including outcome data by the unblinded treatment group.

Primary Outcome Analyses

We hypothesize that participants randomized to MIAPP + treatment as usual compared to treatment as usual alone will be more likely to link to outpatient treatment with medications for OUD within the 30 days of hospital discharge. To evaluate the primary hypothesis, we will use modified Poisson regression analysis (53) with robust standard errors to compare intervention arms on the proportion of participants who link to outpatient treatment with medications for OUD within 30 days of hospital discharge, while potentially controlling for any baseline variables that differ between the two groups as described above if they could confound the hypothesis test. The results of this analysis will be presented as the proportion of patients in each group who link to outpatient treatment and the (adjusted) risk ratio (RR, i.e., ratio of the two proportions) with a 95% confidence interval computed by exponentially transforming the coefficient of the treatment effect in the modified Poisson regression model. We will also report the difference between proportions with a 95% confidence interval, as recommended by CONSORT guidelines (54). The RR and difference are two different ways of quantifying the intervention effect that have meaningful clinical interpretations. Results from the Poisson regression will be used for primary interpretation and conclusions.

Secondary Outcome Analyses

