We hypothesize that participants randomized to MIAPP + treatment as usual compared to treatment as usual alone will a) have more days of medications for OUD treatment within the 90 days post-discharge (secondary), b) have lower rates of readmissions to the hospital and emergency department visits within 90 days (exploratory), and c) have fewer days using opioids or methamphetamine 30 days post-hospital discharge (exploratory). Analyses of secondary outcomes will use modified Poisson regression similar to those described above for binary outcomes (readmissions to hospital and emergency department) and linear regression for continuous outcomes (e.g., days of medications for OUD treatment; days of opioid or methamphetamine use).

Sample Size and Power

The primary goal of this pilot trial is to develop and pilot test the MIAPP intervention. This pilot work will provide evidence of the feasibility/acceptability of the MIAPP intervention and research procedures that will be used to inform a future, larger study, as assessed by our ability to fully recruit the planned sample and deliver the intervention to the majority of those randomized to the intervention arm. The sample size of 40 for the pilot randomized controlled trial was chosen as we projected we could enroll and complete the study procedures and analyses within the available funding period. Although the sample size was not selected for the purpose of providing a fully-powered study, with our sample size of 40 we are nonetheless powered at 80% to detect some effects if they are large in size. For binary outcomes, power depends on the base rate of the outcome measured, and based on prior studies (38, 55), we anticipate that anywhere from 20% to 50% of participants in treatment as usual successfully linking to outpatient medications for OUD services post-discharge. For binary outcomes, including the primary outcome measure, our pilot study will be powered to detect intervention effect sizes of $RR \geq 1.89, 2.05, 2.40, \text{ or } 3.10$, if linkage rates for treatment as usual are 50%, 40%, 30%, or 20%, respectively.

For continuous outcomes (days of buprenorphine coverage, days of opioid or methamphetamine use), we will be powered to detect standardized effect sizes of Cohen's $d \geq 0.91$ with 40 participants.

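### With 20 per arm, the modified Poisson Wald test and interval are conservative and break down when an arm has no events; a score method should carry the unadjusted inference for binary outcomes

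*Combined protocol and SAP*

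**What the plan says.** The section on involvement of human subjects fixes the size: "Patients will be assigned to one of two arms (20 per arm) using a stratified randomization procedure". For the primary outcome, linkage within 30 days, the Primary Outcome Analyses section states that "we will use modified Poisson regression analysis (53) with robust standard errors to compare intervention arms", and the risk ratio is given "with a 95% confidence interval computed by exponentially transforming the coefficient of the treatment effect in the modified Poisson regression model". That is a Wald interval on the log risk ratio. A risk difference with a 95% interval is also promised, with no method named, but "Results from the Poisson regression will be used for primary interpretation and conclusions". The Secondary Outcome Analyses section carries the method over: "Analyses of secondary outcomes will use modified Poisson regression similar to those described above for binary outcomes (readmissions to hospital and emergency department". There the hypothesis is a reduction within 90 days, labelled exploratory.

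Baseline variables that differ between arms and could confound may be added as covariates; no number or limit is given. The plan names no small-sample correction, no score or exact method, and no rule for an arm without events.

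The Sample Size and Power section says that "we are nonetheless powered at 80% to detect some effects if they are large in size" and lists detectable risk ratios of 1.89, 2.05, 2.40 and 3.10 "if linkage rates for treatment as usual are 50%, 40%, 30%, or 20%, respectively". It gives no readmission or ED rate and no detectable reduction.

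**The concern.** The robust Wald statistic relies on a large-sample normal approximation for the log risk ratio. With 20 per arm that approximation is poor when either arm has few events, and it fails when an arm has none. In that case the coefficient drifts to a large negative number while the robust standard error stays finite, so software prints a vanishingly small p-value whatever the other arm shows.

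Two things are at stake. The stated conclusions for linkage rest on a test that runs below its nominal level and so gives up some power. For readmissions and ED visits, if they are uncommon, an analysis run as written could report an overwhelming reduction from a table such as 0/20 v 1/20.

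**Working it through.** **Inputs.** 20 per arm; linkage rates under usual care of 20 to 50% and the four risk ratios (Sample Size and Power). Two-sided 5% is assumed, as the 95% interval implies. Readmission and ED rates are not in the documents and are varied.

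**1. The plan's own figures.** Pooled normal-approximation power is Φ{[|p1−p0| − 1.96√(2p̄(1−p̄)/20)] / √[(p1(1−p1)+p0(1−p0))/20]}. For 40% and RR 2.05: p1 = 0.82, p̄ = 0.61, giving (0.42 − 0.302)/0.139 = 0.845 and power 0.801. The other three give 0.914 (50%, 1.89), 0.779 (30%, 2.40) and 0.794 (20%, 3.10). Three sit near 80%; at 50% the same formula reaches 80% at RR 1.79.

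**2. The tests.** With two arms and no covariates, modified Poisson with the usual (HC0) robust error is

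z = ln(p̂1/p̂0) / √[(1−p̂1)/x1 + (1−p̂0)/x0].

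The comparator is the Pearson score chi-square. The Miettinen-Nurminen version multiplies it by 39/40, which changes no rejection at 20 per arm.

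Example, 1/20 v 6/20:
- Wald: variance = 0.95/1 + 0.70/6 = 1.067, SE 1.033, z = 1.792/1.033 = 1.73, p = 0.083.
- Score: 40(1×14 − 19×6)²/(20×20×7×33) = 4.33, p = 0.037.

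Against 1/20, the Wald test needs 8/20 in the other arm to reject; the score test needs 6/20.

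**3. Exact size.** Sum the product of two Binomial(20, p) probabilities over the 21 × 21 tables that reject. Tables with an empty arm count as non-rejections for the Wald test here.

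| Event rate | Wald | Score |
|---|---|---|
| 20% | 0.8% | 5.0% |
| 30% | 2.3% | 5.3% |
| 40% | 3.5% | 4.8% |
| 50% | 3.9% | 4.3% |

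**4. Exact power, same convention.**

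| Alternative | Wald | Score |
|---|---|---|
| 50%, RR 1.89 | 0.921 | 0.936 |
| 40%, RR 2.05 | 0.764 | 0.805 |
| 30%, RR 2.40 | 0.750 | 0.760 |
| 20%, RR 3.10 | 0.743 | 0.791 |
| 20% halved | 0.012 | 0.138 |
| 30% halved | 0.073 | 0.205 |
| 40% halved | 0.18 | 0.29 |
| 50% halved | 0.31 | 0.38 |
| 60% halved | 0.44 | 0.46 |

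**5. An empty arm.** Let the fitted mean in the empty arm be m. Each residual is −m, so that arm's robust variance is 20m²/(20m)² = 0.05, however small m becomes. For 0/20 v 1/20 the total is 0.05 + 0.95/1 = 1.0, so SE = 1.0. The coefficient stops where the algorithm stops, here −20.4, and p = 2e-92. For 0/20 v 3/20 the printed p is 2e-300; Fisher's test gives 0.23. For 0/20 v 1/20 the score chi-square is 40(0×19 − 20×1)²/(20×20×1×39) = 1.03, p = 0.31.

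Under the null, the chance that exactly one arm is empty is 2(1−p)²⁰[1−(1−p)²⁰]:
- p = 20%: 2 × 0.0115 × 0.988 = 2.3%
- p = 15%: 2 × 0.0388 × 0.961 = 7.5%
- p = 10%: 2 × 0.1216 × 0.878 = 21%

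At 30% it is 0.16%. If those fits are taken as printed, the size is 3.1%, 7.7% and 21% at 20, 15 and 10%.

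**6. Covariates.** Two simulations with four assumed prognostic covariates and the uncorrected robust error gave a type I error of 7.0% and 7.7% at a 20% rate, and between 5.5% and about 6% at 30 to 50%. An HC2 error gave 3.6% to 4.6%. With 4,000 runs the simulation error is about 0.4 points.

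**The case against.** The strongest reply is that this is a 40-person feasibility pilot. The plan says the sample was not chosen for full power, calls readmissions and ED visits exploratory, and expects linkage of 20 to 50%, where an empty arm is rare. For linkage the loss is only 1 to 5 points of power, and the test errs on the safe side: with empty-arm tables excluded, its unadjusted size never exceeds 4.9%. The arm proportions and risk difference are also reported for the primary outcome, so a reader would see 0/20 v 1/20. All of this stands. It limits the harm for linkage but supplies no rule for an empty arm in the readmission and ED analyses.

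A reader might infer that the method leaves almost no power for reductions in readmissions or ED visits. The documents do not support that as a general statement. They give no base rate, and Wald power for a halving is 31% at 50% and 44% at 60%. Much of the weakness comes from n = 40: the score test also has only 14% to 46% for a halving across 20 to 60%.

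The liberal direction is also soft. The plan only says covariates might be added; four, and their prognostic strength, are assumptions, and 6% is a slight excess.

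**Conclusion.** The point holds in a limited form. Unadjusted, the planned Wald test is conservative, with size 0.8% to 3.9% at rates of 20 to 50%, where the score test has 4.3% to 5.3%. For linkage this is a modest loss of power. For uncommon events the loss is larger, and an empty arm yields a printed result with no meaning. How often that happens depends on readmission and ED rates the documents do not give: it matters at about 20% or below and hardly at all from 30% up. Adjustment with an uncorrected robust error may make the test mildly liberal, about 6 to 8% under an assumed four prognostic covariates.

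It would go too far to say that the plan's intervals and p-values are wrong in both directions. The conservative side is exact; the liberal side rests on an assumed covariate set or on accepting empty-arm fits as printed. Low power for readmissions and ED visits is mainly a matter of sample size, which the plan discloses, and forms no part of this conclusion. The exact figures assume 20 analysed per arm and no covariates.

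**What to change.** In the SAP, for the primary and all other binary outcomes:

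- Take the unadjusted p-value and the 95% intervals for both the risk ratio and the risk difference from the score (Miettinen-Nurminen) method. The unstratified form is the one checked here; the documents mention stratified randomisation but never name the strata.
- Keep modified Poisson only for the adjusted risk ratio, with an HC2-type small-sample robust error.
- When an arm has no events, do not report the Poisson risk ratio, interval or p-value; report the score interval alone. No such rule is needed when all 20 in an arm have the event, because that fit behaves normally (20/20 v 19/20 gives p = 0.32).
- Amend the sentence that rests conclusions on the Poisson regression to match.

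The cost is a change of SAP wording and standard software. The drawback is that the score test's exact level can slightly exceed 5%, to about 5.3%. The change does not make the exploratory comparisons well powered.

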Research assessments will occur at baseline during hospitalization and 30 days after discharge from the hospital (“30-day follow-up”). Both assessments will ideally be in-person visits, with research staff administering assessments in an interview format. Point-of-care urine drug testing using Alere 14 Panel Drug Test iCup DX or equivalent will be administered at the 30-day follow-up visit only. Study data (including screening, assessment, urine drug testing results) will only be recorded for research purposes and will not be shared with clinical providers outside of the study team (unless there are imminent safety concerns). Participants will be reimbursed \$60 for the baseline visit and \$60 for the 30-day follow-up visit, plus another \$20 at the 30-day follow-up visit if a urine drug test is provided. This reimbursement for study participation will be provided to both study arms (MIAPP and control arm). At the 30-day follow-up visit, participants will return any study-provided smartphones, if utilized. Data extraction for secondary outcomes will occur after 180 days, which will encompass the 30-, 90-, and 180-day outcome timepoints we will report. These secondary outcomes will include outpatient visits/medications, hospital readmissions, and emergency department visits and will be obtained through partnership with WA State DSHS RDA. Data will be collected for patients who are enrolled in the pilot RCT (Aim 1), as well as for a larger, historical, observational cohort of HMC patients who initiated

treatment with buprenorphine between 2019 and 2021 (Aim 2). This will ensure the feasibility of collecting outcomes for a larger sample size and provide estimates of rates of healthcare utilization that can be used to power a larger clinical trial.

Eligibility

Inclusion Criteria:

- ≥ 18 years old
- Admitted to HMC on any inpatient service
- Initiated on sublingual buprenorphine for OUD while in the hospital or at the time of discharge and planning to continue outpatient
- Used methamphetamine within the past 30 days (any route of administration or frequency), per patient self-report at screening
- Willing to be randomized to MIAPP intervention or control condition
- Willing and able to use a smartphone (study can provide) and work with patient navigator
- Discharge setting does not preclude the use of video-DOT (i.e., nursing home, inpatient psychiatry, etc.)

Exclusion Criteria:

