Individuals who are eligible and enroll in the RCT will complete a baseline and a 30-day post-discharge study visit. Data to be collected at those visits include information on demographics, co-morbidities, current and past addiction treatment, medication adherence and knowledge, motivation and skills for adherence, current and past-year substance use, HIV risk behaviors, mental health symptoms, and satisfaction and trust in provider (both for physician and patient navigator). Urine drug testing will occur at the 30-day post-discharge visit using Alere 14 Panel Drug Test Cup iCup DX or equivalent multi-drug point-of-care test, and a fentanyl urine test strip. A review of medical records (electronic and faxed records from outside hospitals) will be conducted to record information on hospital readmissions and outpatient treatment for 90 and 180 days post-discharge. Assessment data will be collected directly onto netbook computers used by research assessors. We will utilize the Research Electronic Data Capture (REDCap) system through the University of Washington's Institute of Translational Health Services (ITHS). Hospital readmissions and Emergency Department visits within 90 and 180 days of discharge will be extracted by WA State DSHS RDA from statewide Medicaid claims data.

Consent Procedures

The informed consent process will be conducted by staff members trained in the ethical treatment of human subjects. This process involves presenting a detailed verbal description of the study as it is described on the printed, IRB-approved consent form. Subjects will be advised of the purpose of the research and will be asked to provide their verbal informed consent for screening. Answers will be recorded anonymously. Eligible subjects will then be informed of the details of the study and will provide written consent if they wish to participate. Research assessors will review the elements of consent with participants, including the purpose and duration of the study; a description of the study procedures; the risks, discomforts, and benefits; the procedures to ensure confidentiality (including use of unique, non-personally identifying ID numbers instead of names on research materials and maintenance of data in protected computer databases and locked filing cabinets in locked rooms); and that participation is voluntary and their decision whether or not to participate will not impact their clinical care in any way.

Risks to Human Subjects

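### Adjustment for baseline use is not prespecified for the exploratory days-of-use outcomes; it depends on an observed imbalance between arms, which forgoes most of the precision available.

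*Combined protocol and SAP*

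**What the plan says.** The section Secondary Outcome Analyses hypothesises that the intervention arm will "have fewer days using opioids or methamphetamine 30 days post-hospital discharge (exploratory"). The planned method is "linear regression for continuous outcomes (e.g., days of medications for OUD treatment; days of opioid or methamphetamine use"). No covariate is named there.

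The opening paragraph of the Statistical Analysis Plan sets a covariate rule for all analyses. First, "variables will be assessed for any differences between the two randomized arms using chi-square tests, t-tests, or the Mann-Whitney U test", depending on distribution. Then: "Baseline variables that differ between the two arms and potentially confound tests of intervention effects will be included in analyses as covariates". No significance threshold is given for deciding that a variable differs.

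Research Material Obtained from Participants lists what the baseline and 30-day visits collect, including "motivation and skills for adherence, current and past-year substance use, HIV risk behaviors, mental health symptoms". It gives no unit or window for substance use. The inclusion criteria require recent methamphetamine use: "Used methamphetamine within the past 30 days (any route of administration or frequency), per patient self-report at screening". That is a yes/no item, not a stated count of days.

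Sample Size and Power gives a detectable Cohen's d of 0.91 or more for continuous outcomes, "with 40 participants", and names days of opioid or methamphetamine use among them.

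**The concern.** A participant's earlier use is the natural candidate predictor of later use. Including it as a covariate removes the part of the outcome variance that it explains, and with it the part of the error in the treatment estimate that comes from chance imbalance in earlier use. That gain does not depend on the arms looking different at baseline, so a rule that waits for a visible difference mostly misses it.

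What is at stake is the width of the interval for an exploratory outcome. The trial is meant to inform a larger study and, on its own figures, has 80% power only for large effects, so a narrower interval at no extra recruitment is worth having. The rule also leaves the final model undetermined until the baseline tests have been run.

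**Working it through.** **Inputs**
- 20 per arm, 40 in total (Overview of Screening and Recruitment).
- 80% power and d = 0.91 (Sample Size and Power).
- Two-sided alpha 0.05: not stated, assumed; it fits the 95% intervals planned for the primary outcome.
- Correlation r between baseline and 30-day use: not in the documents, so a range is shown.
- Normal outcome and no dropout: assumed.

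**1. Reproduce the plan's figure.** For a two-sample t-test, the noncentrality is d × sqrt(n/2) = d × sqrt(10), with 38 degrees of freedom. Solving for 80% power gives d = 0.909; power at d = 0.91 is 80.1%. The stated 0.91 is therefore the unadjusted figure with all 40 analysed. With fewer completers it rises, to 0.96 at 18 per arm and 1.02 at 16 per arm.

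**2. How often the conditional rule acts.** Under randomization, a baseline test at p<0.05 is significant about 5% of the time (4.8% to 5.3% in simulation). The standard error of the difference in baseline means is sqrt(2/20) = 0.316 SD, so significance needs a gap of about 2.02 × 0.316 = 0.64 SD. Smaller gaps go unadjusted. A looser threshold would bring the covariate in more often; the requirement that it could confound can only reduce that.

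**3. What the rule recovers.** Simulation, 8,000 trials per setting, 20 per arm, true d = 0.91:

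| r | Never adjust | Conditional rule | Always adjust |
|---|---|---|---|
| 0.3 | 81.0% | 81.0% | 83.1% |
| 0.5 | 80.3% | 81.2% | 88.8% |
| 0.7 | 80.4% | 82.2% | 97.4% |

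With no true effect, the conditional rule rejects in 4.9%, 4.6% and 3.4% of trials at these correlations. Always adjusting stays at 5.1% to 5.3%.

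**4. Detectable effect with prespecified adjustment.** One covariate leaves 37 degrees of freedom, for which the detectable d before any variance reduction is 0.910. The residual SD shrinks by sqrt(1 − r²). Estimating the slope inflates the expected variance by 1 + 1/(40 − 4) = 37/36, a factor of 1.014 on the SD. So

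d = 0.910 × sqrt(1 − r²) × 1.014.

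At r = 0.5, for example, 0.910 × 0.866 × 1.014 = 0.80.

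| r | Detectable d, 80% power |
|---|---|
| 0 | 0.92 |
| 0.2 | 0.90 |
| 0.3 | 0.88 |
| 0.4 | 0.85 |
| 0.5 | 0.80 |
| 0.6 | 0.74 |

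**5. Break-even.** The variance is unchanged when (1 − r²) × 37/36 = 1, so r² = 1/37 and r is about 0.16.

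**The case against.** The strongest reply is that the SAP already provides for baseline adjustment. A reader might infer that these outcomes will be analysed without their baseline values; the documents do not support that, because the general rule can admit baseline use when the arms differ. What remains is that admission is conditional and, on the arithmetic above, rare.

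Several other points limit the weight of the concern, and they stand.
- The outcome is labelled exploratory, and the plan says that its sample size was not chosen to give a fully powered study.
- The correlation is unknown. Baseline use precedes hospitalization and buprenorphine initiation, and every participant must be a recent methamphetamine user, so a low value is plausible. Below about 0.2 the gain is negligible.
- The documents do not say that baseline use is counted in days, over a matching window, or separately by substance. The only timeline follow-back they describe concerns buprenorphine adherence at the final visit.

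Three stronger readings are also tempting. One is that the unadjusted comparison is biased: under randomization it is not, and adjustment removes only the error due to the imbalance that happened to occur. Another is that effects below 0.91 cannot be detected: 0.91 is the 80% power point, and unadjusted power at d = 0.8 is still about 69%. The third is that the conditional rule inflates false positives: in the simulation it made the test slightly conservative.

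**Conclusion.** The point holds in a limited form. Baseline use is collected in some form, but adjustment for it is left to an imbalance check instead of being prespecified. If that check is p<0.05, it acts in about 5% of trials and recovers about 1 of the roughly 8 percentage points of power available at r = 0.5. Prespecified adjustment lowers the detectable d from 0.91 to between 0.90 and 0.74 for r from 0.2 to 0.6, and raises it to 0.92 if r is zero.

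These figures rest on an assumed threshold, assumed correlations, a normal outcome and complete follow-up. They include no term for stratification: Involvement of Human Subjects says that randomization is stratified but names no factor. A reader might infer that the trial's main conclusion is at risk. It is not: linkage within 30 days is a separate binary outcome that this change does not touch. Priority is low.

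**What to change.** Add one sentence to Secondary Outcome Analyses: for opioid use and methamphetamine use separately, fit linear regression of the 30-day outcome on arm and the participant's baseline use of the same substance, as recorded at the baseline interview, whatever the observed balance. Make the change before any outcome data are analysed by arm.

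First check the baseline form for the scale on which use is recorded. If days over a window matching the outcome are available, use those; if not, use the closest measure collected and say so in the SAP.

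The cost is that check, one sentence and one degree of freedom, with a trivial loss of precision if the correlation turns out to be below about 0.16. No extra participants or visits are needed.

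### The four stated detectable risk ratios do not come from any one method tried, and the planned modified Poisson test falls short of 80% power at three of them

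*Combined protocol and SAP*

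**What the plan says.** The Sample Size and Power section states that "with our sample size of 40 we are nonetheless powered at 80% to detect some effects if they are large in size". For binary outcomes, the primary one included, it gives minimum risk ratios of "1.89, 2.05, 2.40" and 3.10, "if linkage rates for treatment as usual are 50%, 40%, 30%, or 20%, respectively". It names no test, alpha or sidedness for these figures. The same section says that the sample size was set by what could be enrolled within the funding period, not to provide a fully powered study.

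The test is defined in the Primary Outcome Analyses section: "we will use modified Poisson regression analysis (53) with robust standard errors to compare intervention arms". The risk ratio is to be reported "with a 95% confidence interval computed by exponentially transforming the coefficient of the treatment effect in the modified Poisson regression model", and "Results from the Poisson regression will be used for primary interpretation and conclusions". Allocation is given under Involvement of Human Subjects: "Patients will be assigned to one of two arms (20 per arm").

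**The concern.** Multiplying each TAU rate by its risk ratio gives the intervention-arm rate that the sentence implies: 94.5%, 82%, 72% and 62%. The last three are each exactly 42 percentage points above TAU, whereas the first is 44.5 points above. This pattern suggests that the first figure was not obtained in the same way as the others.

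The second question is whether the figures describe the test that will be used. A two-proportion formula and a Wald test on the log risk ratio can differ noticeably at 20 per arm. If the figures belong to the former, the 80% claim need not hold for the latter. What is at stake is the accuracy of a stated power figure for the primary outcome.

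**Working it through.** **Inputs.** 20 per arm (Involvement of Human Subjects). TAU rates p0 of 0.50, 0.40, 0.30 and 0.20, the four stated risk ratios, and 80% power (Sample Size and Power). All 20 per arm are analysed, because the plan is intent-to-treat and the power statement allows for no dropout. Two-sided 5% is an assumption. It is supported by the 95% confidence interval in Primary Outcome Analyses and by the stated Cohen's d of 0.91, since a two-sided 5% t-test with 20 per arm gives 0.909.

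**Step 1: reproduce the plan's figures with a two-proportion formula.** With p1 = p0 × RR and p̄ the mean of p0 and p1, the pooled z formula is

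power = Φ{ [p1 − p0 − 1.96 √(2p̄(1 − p̄)/n)] / √([p0(1 − p0) + p1(1 − p1)]/n) }.

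- At 40%, p1 = 0.82: (0.42 − 1.96 × 0.1542)/0.1392 = 0.845, so power is 80.1%. The stated 2.05 reproduces.
- At 50%, p1 = 0.945: (0.445 − 1.96 × 0.1416)/0.1229 = 1.363, so power is 91.4%. The stated 1.89 does not reproduce.

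Risk ratio giving 80% power, by method:

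| TAU rate | 50% | 40% | 30% | 20% |
|---|---|---|---|---|
| Stated | 1.89 | 2.05 | 2.40 | 3.10 |
| Pooled z | 1.79 | 2.05 | 2.43 | 3.12 |
| Arcsine | 1.78 | 2.04 | 2.43 | 3.10 |
| Continuity-corrected z | 1.87 | 2.16 | 2.59 | 3.37 |
| Fisher exact | 1.84 | 2.13 | 2.60 | 3.36 |
| Log-RR delta method | 1.90 | 2.22 | 2.72 | 3.70 |

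Power at the stated values is 91.4%, 80.1%, 77.9% and 79.4% by pooled z, and about 93%, 81%, 78% and 80% by arcsine. The methods that come near 1.89 miss the other three. Other exact and approximate tests, one-sided 5% for the main methods, and 16 to 19 per arm were also tried. None gave all four values.

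**Step 2: exact power of the planned test.** Without covariates, the modified Poisson estimate is ln(y/x) for x and y linked out of 20 in the TAU and intervention arms. Its robust variance is (1 − x/20)/x + (1 − y/20)/y. This closed form was checked against a fitted Poisson model with robust errors. The test rejects when |ln(y/x)| divided by the standard error exceeds 1.96. Binomial probabilities were summed over all 21 × 21 outcomes. The estimate is undefined when an arm has no events, so such tables were counted first as non-rejections and then as rejections.

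| TAU rate | 50% | 40% | 30% | 20% |
|---|---|---|---|---|
| Power at stated RR | 92.1% | 76.4% | 75.0% | 74.3–75.4% |
| RR for 80% power | 1.81 | 2.09 | 2.48 | 3.21–3.24 |

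Replacing 1.89 with 1.79 would not rescue the first figure for this test, because exact power at 1.79 is 77.5%.

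**Step 3: sensitivity.** With a small-sample variance correction and a t critical value, power at the stated values falls to 88.0%, 71.2%, 64.6% and 65.0–66.1%. At one-sided 5%, the planned test would reach about 84 to 86% at the three lower TAU rates, so the shortfall depends on the two-sided reading. The test's true type I error at 20% TAU is 0.8% or 3.1%, depending on how zero-event arms are counted, and should not be quoted as a single number.

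**The case against.** The strongest reply is that little turns on this. Three of the four figures do fit a standard formula. The fourth errs on the safe side: the trial has more than 80% power at 1.89. For the planned test, reaching 80% moves the detectable intervention rate from 82% to 83.5% (0.40 × 2.087), from 72% to 74.3% (0.30 × 2.478) and from 62% to at most 64.7% (0.20 × 3.236). Each shift is under 3 points, while one patient in 20 is 5 points. The section claims power only for large effects, and the sample size rested on feasibility. All of this stands, and it limits the point to a minor correction. It does not make the sentence right, because the plan attaches 80% to specific values for the primary outcome.

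A reader might infer more than the documents support:

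- **That none of the figures can be reproduced.** Three can, approximately.
- **That 1.89 is a misprint for 1.79.** This is plausible but cannot be shown. The delta-method formula gives 1.90 at 50%, so the origin of the figure is unknown.
- **That the figures will mislead the larger trial or the reading of a null result.** Nothing in the documents carries these risk ratios into the later design. The pilot informs it through feasibility, and the Data Collection Overview names healthcare utilization rates as the input for powering it. What a null result excludes will come from the planned confidence intervals.

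**Conclusion.** The sentence is wrong as written in two limited ways. First, 1.89 is inconsistent with the other three figures under every method tried. The expected value is 1.78 to 1.79 by the formulas that fit the others, and the error is conservative. Second, the planned primary test has about 76%, 75% and 74 to 75% power at the values stated for TAU rates of 40%, 30% and 20%, a shortfall of roughly 4 to 6 points from the stated 80%.

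This rests on 20 evaluable per arm, two-sided 5%, no covariate adjustment, and the uncorrected robust variance with a normal critical value. The plan does not say which variance form will be used and allows adjustment for baseline differences, so the replacement values are approximate. It does not follow that the trial is too small for its stated purpose or that the primary test should be changed. The severity is minor.

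**What to change.** In the Sample Size and Power section, state the test, alpha and sidedness, and replace all four risk ratios with values from one method that matches the planned analysis. For the unadjusted modified Poisson test with robust standard errors at two-sided 5% and 20 per arm, these are about 1.81, 2.09, 2.48 and 3.21 to 3.24 at TAU rates of 50%, 40%, 30% and 20%. Say how a zero-event arm is handled, since the last value depends on it. If a small-sample variance correction with a t critical value is intended, say so and recompute, because the values rise further.

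Keep the planned primary test. Moving to a score-based test and interval would be a trade-off against the regression adjustment the plan allows, and this point does not require it.

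The cost is a small edit to the power paragraph. Three figures become slightly less favourable and one slightly more so. No patients are added and nothing in the conduct of the trial changes.
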